7.5.2 Buffalo Concussion Bicycle Test

The BCBT measures the exacerbation of post-concussive symptoms during 15 minutes of graded exercise.

The subject will be fitted with the Caretaker4® device which attaches to right arm and right finger and measures continuous beat to beat HR and BP. Once connected, 5 minutes of baseline data collection will occur, during this time, the subject will record their rating of perceived exertion (RPE) on a scale of 6 to 20, and symptom severity using a 10--point visual analog scale.

Exercise will be initiated, and at each minute RPE and symptom severity will be recorded and the bike grade increased to next stage. This will be repeated every minute until termination by:

- Maximum exertion (i.e., exhaustion);
- Three-point increase in symptom severity compared to pre-test, addition of new symptom, or increase in severity resulting in difficulty continuing test;
- Rapid progression of complaints, subject appears faint or unsteady or staff determines inability to continue test safely.

On completion of the exercise, subjects will complete a 5-minute cool down (if safe to do so), during which RPE and symptom severity assessment will continue at 1-minute intervals.

7.6 Evaluation of Neck Range and Motion

The evaluation of neck range and motion will be performed using 2 different tests. The neurologic examination will be completed first followed by the ClearNeck© assessment.

7.6.1 Whiplash Test (Whiplash Testing (ClearNeck©))

The ClearNeck© is ANSwers Neuroscience Pty Ltd commercial prototype for cervico-genic proprioception measurement. The subject will be seated 40 to 50 cm from a bullseye target, and the ClearNeck© (cap with inbuilt laser) will be placed on the subject's head. During testing, the subject will direct the laser onto the target from zero angle (by looking straight ahead with eyes open), and 8 trials (4 left and 4 right) of proprioception (eyes closed, rotate head 90 degrees to the left or right, then back to starting point).

7.6.2 Neurologic Examination

The neurologic examination, by an allied health professional, will include performing the following neurological tests:

- Orthostatic Vital signs: Blood pressure, Heart Rate and Symptoms are measured Supine after 2 minutes rest and Standing after 1 minute rest. Test results are deemed clinically significant if they include at least one of the following AND symptomatic: (1) systolic BP drop of ≥ 20 mmHg or (2) diastolic BP drop of ≥ 10 mmHg.
- Neck and Sub-Occipital Region Exam: Evaluation of neck muscle spasm, tenderness, and range of motion, to evaluate for any signs or symptoms of whiplash
- Oculomotor/Ophthalmologic Evaluation: Evaluations of visual tracking, smooth pursuits, repetitive saccades, gaze stability, and near point of convergence (NPC) and accommodation.
- Postural Control and Motor Coordination: Evaluation of tandem gait with eyes open and closed, and tandem stance.

7.7 Post Study Survey

On completion of the study only, subjects will be invited to comment on study participation and provide suggestions for improvement. Subjects will also be asked to provide a summary of school or work absence during study.

8 STUDY SCHEDULE OF EVENTS

8.1 Order of Assessments

The order of assessment for each subject is dependent on their assigned subject identification numbers. Refer Table 4 for detail.

Table 4: Order of Assessments :

Subjects Assigned to ODD numbered subject identification numbers	Subjects Assigned to EVEN numbered subject identification numbers
Biomarker sample collection	Biomarker sample collection
Ice Bucket Test	ClearHeart©
Neuropsychology Testing (CAARS, CES-D, BAI, ASI [Pre/Post mTBI], BSI-18 [Pre/Post mTBI]).	Neuropsychology Testing (CAARS, CES-D, BAI, ASI [Pre/Post mTBI], BSI-18 [Pre/Post mTBI]).
Neurologic Evaluation	Neurologic Evaluation
ClearNeck©	ClearNeck©
ClearHeart©	Ice Bucket Test
Buffalo Concussion Bike Test	Buffalo Concussion Bike Test
Randomize subject to Exercise or Stretching Group	
Dispense i-touch or i-phone with appropriate software loaded (whether randomized to graded exercise vs. passive stretching). Subject to enter test PCSS and Godin score via ClearPlay App©; to ensure subject is able to use this App.	Dispense i-touch or i-phone with appropriate software loaded (whether randomized to graded exercise vs. passive stretching). Subject to enter test PCSS and Godin score via ClearPlay App©; to ensure subject is able to use this App.
Adverse Events	Adverse Events

Post-study survey to be completed at Day 56 only

Abbreviations: ASI = Anxiety Sensitivity Index, BAI = Beck Anxiety Inventory, BESS = Balance Error Scoring System, BSI = Brief Symptom Inventory, CAARS = Conners' Adult Attention Deficit Hyperactivity Disorder Rating Scale, CES-D = Center for Epidemiologic Studies - Depression Scale, DNA = deoxyribonucleic acid, PCSS = Post-Concussion Symptom Scale, RNA = ribonucleic acid, VOMS = Vestibular-Oculomotor Screening

Table 5: Schedule of Events

Study Assessments	Baseline Visit		Therapy Period	Telephone Safety Visit	Follow-Up/ET
	Day 0 (within 3 to 14 days of concussion)		Day 1 to Day 55	Day 14, Day 28, Day 42 (± 2 days)	Day 56 (± 3 days)
	Screening Evaluation	Study Evaluation			
Study Assessments					
Informed consent	X				
Allocate unique subject study identification	X				
Inclusion/exclusion criteria review	X				
Demographic data	X				
Medical and medication history	X				
Review of CT or MRI (if obtained)	X				
Height and weight ^a	X				X
Subject Completed Questionnaires					
Post-Concussion Symptom Scale (pre- and post-mTBI)		X	X		
Godin leisure time exercise questionnaire ^b		X	X		X
Brief Symptom Inventory (pre- and post-mTBI)		X			X ^f
Anxiety Symptom Index (pre- and post-mTBI)		X			X ^f
Beck Anxiety Inventory		X			X
CAARS (Attention)		X			
CES-D (Depression)		X			

CONFIDENTIAL

Study Assessments	Baseline Visit		Therapy Period	Telephone Safety Visit	Follow-Up/ET
	Day 0 (within 3 to 14 days of concussion)				
	Screening Evaluation	Study Evaluation	Day 1 to Day 55	Day 14, Day 28, Day 42 (±2 days)	Day 56 (±3 days)
Post-study survey					X
Autonomic Tests					
Ice Bucket Testing		X			X
ClearHeart© Testing		X			X
Buffalo Concussion Bike Test		X			X
Other Physical Tests					
ClearNeck© Testing		X			X
Neurologic Testing		X			X
Biomarkers/BioBank					
Biomarker sample collection		X			X
DNA and RNA sample collection		X			X ^d
Therapeutic Intervention					
Dispense i-touch or i-phone.		X			
Waveband® – dispense and instruct		X			
ClearPlay© - dispense and instruct via initial entry of PCSS and Godin data on i-touch or i-phone		X			
Enter/Review ClearPlay© mobile application entries			X ^e		
Return of Waveband®					X

CONFIDENTIAL

Study Assessments	Baseline Visit		Therapy Period	Telephone Safety Visit	Follow-Up/ET
	Day 0 (within 3 to 14 days of concussion)		Day 1 to Day 55	Day 14, Day 28, Day 42 (±2 days)	Day 56 (±3 days)
	Screening Evaluation	Study Evaluation			
Safety Assessments					
Vital signs including beat to beat BP		X			X
Adverse event monitoring		X	X	X	X
Concomitant medications		X	X	X	X
Concomitant therapies		X	X	X	X

Abbreviations: AE = Adverse Event, ASI = Anxiety Sensitivity Index, BAI = Beck Anxiety Inventory, BESS = Balance Error Scoring System, BP = blood pressure; BSI = Brief Symptom Inventory, CAARS = Conners' Adult Attention Deficit Hyperactivity Disorder Rating Scale, CES-D = Center for Epidemiologic Studies - Depression Scale, CT = DNA = deoxyribonucleic acid, , ET = early termination, MRI = magnetic resonance imaging, mTBI = mild traumatic brain injury, PCSS = Post-Concussion Symptom Scale, RNA = ribonucleic acid, VOMS = Vestibular-Oculomotor Screening

Footnotes for Table 5

- Height will only be captured at the Screening Visit;
- Godin leisure time exercise questionnaire to be administered weekly;
- Optional consent required;
- RNA collection only;
- Site to monitor AEs and symptom escalation. Subjects who do not upload data for 3 consecutive days are to be contacted. Subjects who do not upload data for 5 consecutive days are to be contacted again. Subjects who do not upload for 7 consecutive days are to be withdrawn from the study for poor compliance.
- Questionnaires to be completed at Day 56, based on subject's current condition.

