4.2 Study Objectives and Endpoints

The study objectives and endpoints to be evaluated in this study are presented in Table 1.

Table 1: Study Objectives and Endpoints

Objectives	Endpoints
Primary Objectives	Primary Endpoints
To compare the effects of graded exercise to passive stretching using ClearPlay© on symptomatic recovery rate following mTBI.	
 • Within-subject analysis of change in symptoms over time using the PCSS, comparing short-term ‘survival rates’ between graded exercise and stretching using Kaplan-Meier analyses for days since concussion.
Secondary Objectives	Secondary Endpoints
To compare the safety and tolerability of graded exercise to passive stretching in patients following mTBI.	
 • Adverse events reported from Day 1 through Day 56, including those identified during exercise or passive stretching during the 20 minutes of daily therapy.
To compare symptom resolution following graded exercise compared to passive stretching using ClearPlay© following mTBI.	
 • Within subject analysis of change in the number of subjects who are symptom free at 8 weeks between the 2 groups. Symptom free is defined by subjects having 3 consecutive days of PCSS scores lower than pre-concussion. 
Note: This objective is similar to the primary one, with the primary endpoint being recovery (binary outcome) vs. symptom resolution (continuous variable).
 
 • Determine differences in symptomatic recovery based on gender, baseline scores on the PCSS, baseline athletic fitness (Godin leisure-time exercise questionnaire), the history of injury, a history of migraine, as well as the presence of pre-morbid anxiety.
To compare the effects of graded exercise to passive stretching using ClearPlay© on physiologic recovery rate following mTBI.	
 • Within subject analysis of normalization of physiologic measurements obtained during the BCBT comparing data collected on entry to the study on Day 0 vs. follow up on Day 56 including: 
 - Beat to beat BP; • Determine differences in physiologic recovery based on gender, baseline scores on the PCSS, baseline athletic fitness (Godin leisure-time exercise questionnaire), the history of injury, a history of migraine, as well as the presence of pre-morbid anxiety (BAI; BSI-18; ASI).

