5.3 Withdrawal and Replacement of Subjects

5.3.1 Reasons for Withdrawal of Subjects

Subjects will be informed that they have the right to withdraw from the study at any time for any reason, without prejudice to their medical care. The investigator also has the right to withdraw subjects from the study for any of the following reasons:

- Subject non-adherence to therapeutic intervention or protocol requirements. Please refer to Section 6.5 for lifestyle and dietary study restrictions. Subjects must also be able to upload data via the ClearPlay© mobile application daily. Failure to do so for 3 consecutive days will trigger a call from the site. Subjects who do not upload data for 5 consecutive days are to be contacted by the site again. Subjects who do not upload for 7 consecutive days are to be withdrawn from the study for poor compliance;
- Subjects from either group who exercise at a rate that exceeds that which is prescribed, as identified by either self-report (the Godin Leisure Time Exercise questionnaire) or by autonomic monitoring (using ClearPlay©) will be withdrawn from the study and coded as “lost to follow up”.
- Subject unwillingness to continue in the study;
- Any other reason based upon the medical judgment of the investigator.

The reason for study withdrawal is to be documented in the subject’s source documents and electronic case report form (eCRF).

At the time of discontinuation from the study, subjects are to have all the assessments planned for the follow-up visits performed after the last study drug dose, if feasible.

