6 THERAPEUTIC INTERVENTION

6.1 Therapeutic Interventions Administered

The therapeutic intervention (graded exercise) to be used in this study is delivered through the ClearPlay© application. This application will be preloaded on the i-touch or i-phone device, which will be supplied to each eligible subject during the Baseline Visit. ClearPlay© provides the subject with a graded exercise program or passive stretching, which is used in conjunction with a wrist-worn HR monitoring device (Waveband®).²⁹

Each subject will cease their assigned Therapeutic Intervention when they have reach three consecutive days of PCSS score that is less than or equalled to the subject's pre-mTBI PCSS score. All subjects will be required to complete the Follow Up, Day 56 Visit, regardless of the date they cease Therapeutic Intervention.

Table 2: Therapeutic Interventions

Therapeutic Intervention	Description	Duration	Frequency
Telemetry-based graded exercise	Sub-symptom threshold aerobic exercise	20 minutes	Daily for 8 weeks
Passive stretching	Passive stretching	20 minutes	Daily for 8 weeks

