9.6 Efficacy Analysis

The full presentation of the analysis of efficacy data will be presented in the SAP.

For all subjects, daily reported PCSS scores collected from ClearPlay© mobile application will be utilized to determine the resolution of symptoms. The resolution of symptoms is defined as a symptom-severity score of less than each subject's pre-injury PCSS score for 3 consecutive days. To assess differences in the probability of symptom resolution between graded exercise and passive stretching during the 8 weeks of therapy, both unadjusted and adjusted logistic regression models will be used. The primary outcome of the study will be to confirm or refute the superiority of sub-threshold aerobic exercise versus passive stretching to result in resolution of symptoms following mTBI. Confounders for the adjusted models will include age, gender, anxiety at baseline, history of migraine, cardiovascular fitness, the presence or absence of neurologic findings, and site of enrollment.

The survival probability will be compared using Kaplan-Meier (log rank test) analyses between the 2 treatment arms. Cox proportional hazards regression models will be used to evaluate the differences in time to symptom resolution. Adjusted treatment effects will be estimated in Cox proportional hazards regression models, controlling for the variables listed above. To identify that our randomization strategy was effective, analysis of variance will be used to assess for group-wise differences in age, days since injury to initial visit, initial PCSS score, resting HR, and Δ HR during the BCBT and resting BP and Δ BP during the ice bucket test on Day 1. Non-parametric tests of medians will be used to compare the non-normally distributed variable duration of clinical recovery. Chi-squared tests will be used to assess group-wise differences in gender, history of concussions, and incidence of PPCS.

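### The symptom scale that defines the efficacy endpoints is not scheduled at the Day 56/early-termination visit, so subjects who stop uploading or withdraw before resolving have no later score

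*Protocol*

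**What the plan says.** All references are to the protocol.

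- **Schedule (Section 8.1, Table 5).** The row "Post-Concussion Symptom Scale (pre- and post-mTBI") is marked under the Day 0 study evaluation and under the Day 1 to Day 55 therapy period. The telephone column and the Follow-Up/ET column (Day 56, ±3 days) are blank. The row "Beck Anxiety Inventory" and the rows for the Godin, BSI and ASI are all marked under Follow-Up/ET. A footnote asks that the BSI and ASI there reflect the subject's current condition.
- **Endpoint (Section 4.2, Table 1).** A secondary endpoint is the "change in the number of subjects who are symptom free at 8 weeks between the 2 groups". The definition is: "Symptom free is defined by subjects having 3 consecutive days of PCSS scores lower than pre-concussion". The primary endpoint is a Kaplan-Meier comparison, also based on the PCSS.
- **Data source (Section 9.6).** The "daily reported PCSS scores collected from ClearPlay© mobile application will be utilized to determine the resolution of symptoms". Section 7.4.1 has the scale completed daily by each subject.
- **Stopping therapy (Section 6.1).** Therapy stops after three consecutive days at or below the pre-injury score. The section adds: "All subjects will be required to complete the Follow Up, Day 56 Visit, regardless of the date they cease Therapeutic Intervention".
- **Withdrawal (Sections 5.3.1 and 6.4.4).** Seven consecutive days without an upload lead to withdrawal. At discontinuation, "subjects are to have all the assessments planned for the follow-up visits performed", if feasible.
- **Missing data (Section 9.8).** Data up to withdrawal are used, with no imputation unless otherwise stated.

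**The concern.** The PCSS defines both the primary comparison and the count of symptom-free subjects, yet it is missing from the one clinic visit that follows baseline. Section 5.3.1 gives discontinuing subjects the follow-up assessments, so the omission carries over to early termination. A subject withdrawn for not uploading has by construction no recent score, and the visit that could supply one does not ask for it.

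Two things are at stake. The first is whether dropout can be examined: nothing collected on the PCSS would show whether subjects who left before resolving were doing well or badly. The second is the planned correlation between symptom resolution and the Day 0 to Day 56 change in bicycle-test physiology, for which no PCSS is taken at the second time point.

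This cannot be left to the statistical analysis plan. The schedule fixes what is collected, and no analysis can recover a score that was never taken.

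**Working it through.** **1. Reading the schedule against the text**

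| Subject | Scheduled PCSS after the last upload |
|---|---|
| Uploads throughout | Not needed; daily scores run to Day 55 |
| Stops therapy after a three-day run, keeps uploading | Daily scores to Day 55 on the better reading; not stated outright |
| Stops uploading for 7 days before resolving, is withdrawn | None; the Follow-Up/ET column has no PCSS |
| Withdraws for another reason before resolving | None, for the same reason |

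Use of the app does not explain the blank cell. The Godin is also an app instrument (Section 6.2) and is marked both in the therapy period and at Day 56. Table 4 does not fill the gap either: its neuropsychology list omits the PCSS, which appears only as a trial entry when the device is dispensed.

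The visit window adds a small gap. A visit on Day 59 falls 59 − 55 = 4 days after the last scheduled score.

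**2. The protocol's own sample size (Section 9.1)**

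Inputs: 80% and 93% resolution, α = 0.05, power 90%, 1:1 allocation. The protocol does not state sidedness. The two-sided pooled formula is

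n = [1.960·√(2·0.865·0.135) + 1.282·√(0.80·0.20 + 0.93·0.07)]² / 0.13² = 143.1 per arm.

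With continuity correction, (143.1/4)·[1 + √(1 + 4/(143.1·0.13))]² = 158.1. This rounds up to 159 per arm, or 318 in total, against 316 stated, so the figure reproduces closely. The attrition step reproduces as 316 × 1.15 = 363.4; dividing instead gives 316/0.85 = 372. The planned 400 covers either.

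**3. Size of the gap, under an assumption**

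Assume that the 15% attrition in Section 9.1 equals the share of subjects with no final PCSS: 0.15 × 400 = 60, or 30 per arm. This is an upper-end figure, because some subjects will resolve before they leave.

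Power = Φ{[d − 1.960·√(2p̄(1−p̄)/n)] / √([p₁(1−p₁) + p₂(1−p₂)]/n)}, two-sided and without continuity correction. With all 200 per arm observed it gives 97%.

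- *Missingness uninformative, subjects dropped:* n = 170 per arm, 80% against 93%. (0.13 − 0.0726)/0.0364 = 1.58, so power is **94%**.
- *Missing counted as not resolved:* 0.80 × 0.85 = 68.0% and 0.93 × 0.85 = 79.05%, a difference of 11.05 points. With n = 200 per arm, (0.1105 − 0.0865)/0.0438 = 0.55, so power is **71%**.

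| Share with no final PCSS, counted as not resolved | Power, 200 per arm |
|---|---|
| 5% | 90% |
| 10% | 81% |
| 15% | 71% |
| 20% | 62% |

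- *Extreme bounds at 15% missing per arm:* 0.85 × 13 ± 15 points, which is −3.95 to +26.05 points around a planned difference of 13.

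**4. Equality with the pre-injury score**

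Section 6.1 stops therapy at or below the pre-injury score, whereas the Section 4.2 endpoint requires a score below it. A subject who stops on equality has not yet met the endpoint and depends on later daily scores. This is the group for whom it matters that the protocol does not say outright whether entry continues.

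**The case against.** The strongest reply is that the endpoint is an event and not a state on Day 56. A subject is symptom free once three consecutive daily scores fall below the pre-injury value, and Section 9.6 takes this from the app over the 8 weeks. Anyone with such a run has met the endpoint. Anyone who leaves earlier still contributes scores up to that point and can be censored in the Kaplan-Meier and Cox analyses. This stands, and it limits the point to subjects who stop uploading or withdraw before resolving. For them, censoring assumes that leaving is unrelated to symptoms, and a PCSS at the early-termination visit is what would help to check that.

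A reader might infer three stronger things that the documents do not support.

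- *That everyone who stops therapy early has no later score.* Section 6.1 ends only the intervention. Section 7.4.1 has every subject complete the scale daily, and Table 5 runs it to Day 55 without exempting resolved subjects. The 7-day upload rule points the same way: if resolved subjects stopped entering data, early resolvers would be withdrawn, yet all must attend Day 56.
- *That relapse after a qualifying run is missed.* Relapse is not a stated endpoint.
- *That the Day 56 bicycle test has no symptom score from the same day.* Section 7.5.2 records symptom severity on a 10-point scale before exercise and each minute during it. What is absent is the PCSS.

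It is also fair to say that a single added score cannot show three consecutive days, that an early-termination visit well before Day 56 does not give week-8 status, and that this visit happens only if feasible. All three limit what the remedy can do.

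**Conclusion.** The point holds in a narrow form. The PCSS is absent from the Follow-Up/ET column, so subjects who stop uploading or withdraw before resolving have no scheduled PCSS after their last upload, and none is taken at the Day 56 visit. Subjects who upload throughout are covered to Day 55. So, on the better reading, are those who stop therapy and keep entering data, though the protocol should say so.

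The protocol does not say how many subjects would lack a final score. If it were as many as 15% (60 of 400), power would range from about 94% with uninformative missingness to about 71% if missing counted as not resolved. That range rests on treating the attrition allowance as the share without a final PCSS, on the planning rates of 80% and 93%, and on a two-sided comparison of proportions. It shows how much the handling of these subjects can matter; it is not a forecast.

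The omission is worth correcting before data collection because it is cheap to mend and cannot be mended afterwards. The correction would support the endpoint and the assessment of informative dropout, but would not fully repair the endpoint.

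**What to change.** 1. In Table 5, mark the PCSS (current state) under Follow-Up/ET and specify that it is completed before the bicycle test, so that exertion does not influence it.
2. State its use: supportive final symptom status, and sensitivity analyses for dropout. It should not by itself establish resolution.
3. State in Sections 6.1 and 7.4.1 and in Table 5 that daily PCSS entry continues to Day 56 for all subjects, including those who have ceased therapy.
4. Reconcile the therapy-stopping wording in Section 6.1, which includes equality with the pre-injury score, with the endpoint definition in Section 4.2, which does not. Which rule is intended is for the sponsor to decide.

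Cost: one 21-item questionnaire at a visit that already takes place, continued brief app entry for subjects who have ceased therapy, and a few clarifying sentences.
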